**Official title: Effectiveness of a 12-week
Telerehabilitation Training in People with
Long COVID: A Randomized Controlled Trial**

NCT number: NCT05205460

document date: 2023.11.25

Study Protocol with SAP

Background: Long COVID, characterized by persistent symptoms beyond the acute phase of SARS-CoV-2 infection, has been associated with impairments in cardiopulmonary function, physical activity levels, and overall quality of life. Telerehabilitation has emerged as a feasible and effective intervention for individuals with limited access to in-person rehabilitation services.

Objective(s): To investigate the effectiveness of a 12-week telerehabilitation training program, the primary outcome is cardiorespiratory fitness (CRF), with secondary outcomes including physical activity (PA) amounts, exercise self-efficacy, sleep quality, and health-related quality of life (HRQOL) in participants with long COVID.

Design: A parallel-group randomized controlled trial

Methods: A parallel-group randomized controlled trial was conducted. Eligible participants with long COVID ($n = 182$) were randomly assigned in a 1:1 ratio to either the experimental group (EG) or control group (CG). The EG received 12-week telerehabilitation training with weekly remote monitoring for the maintenance of exercise and support. The CG received physical activity (PA) counseling only.

Outcome measures:

primary Outcome: cardiorespiratory fitness (CRF)

secondary Outcomes: exercise self-efficacy, sleep quality, and health-related quality of life (HRQOL)

Statistical analysis plan: Statistical analyses were performed using SPSS version 16.0 software. Descriptive statistics included means with standard deviations for continuous variables and numbers with percentages (%) for categorical variables. Missing data were handled using the last-observation-carried-forward method for intent-to-treat analysis. Paired t-tests were used to compare pre- and post-tests, whereas Student's t-tests and chi-squared tests examined pre- and post-intervention differences between groups. Generalized estimating equations (GEEs) were used to analyze longitudinal data, considering within-participant correlation. All analyses were two-tailed, with $p < 0.05$ indicating statistical significance.

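### LOCF is the only missing-data rule for the ITT analysis and has no sensitivity analysis; unless an unstated interim CRF test exists, a missing post-test becomes zero change, which can bias the primary comparison in either direction

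*Combined protocol and SAP*

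**What the plan says.** The Statistical analysis plan is a single paragraph. Its missing-data rule is "Missing data were handled using the last-observation-carried-forward method for intent-to-treat analysis". No assumption about why data are missing, no expected dropout and no sensitivity analysis accompanies it.

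The assessments it names are a pre-test and a post-test: "Paired t-tests were used to compare pre- and post-tests", and Student's "t-tests and chi-squared tests examined pre- and post-intervention differences between groups". It then adds "Generalized estimating equations (GEEs) were used to analyze longitudinal data, considering within-participant correlation". It does not list the time points in that model, say whether the model used LOCF-filled or observed data, or present the model as a check on LOCF.

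CRF is the primary outcome (Objective(s) and Outcome measures). The Methods paragraph shows that contact differed between arms: "The EG received 12-week telerehabilitation training with weekly remote monitoring for the maintenance of exercise and support", whereas "The CG received physical activity (PA) counseling only".

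**The concern.** With one test before and one after the intervention, the last observation of a participant who misses the post-test is the baseline value. LOCF then records a change of exactly zero. In a trial that asks whether training changes CRF, that is a substantive assumption about the primary outcome, and the plan neither defends nor tests it.

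If the arms lose different fractions of participants and both arms tend to change, the zeros are spread unevenly and can create a difference or hide one. If dropout is equal and dropouts resemble completers, a real effect is diluted. The unequal contact makes unequal dropout plausible, but nothing in the document indicates which arm would lose more. A reader cannot tell from the planned analyses whether the CRF result depends on the zero-change assumption.

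**Working it through.** **Inputs from the document.** 182 participants randomised 1:1 (Methods); two-sided 0.05, LOCF, and pre- and post-tests (Statistical analysis plan). The document gives no power calculation, dropout, SD, effect size or mean change, so there is no planned figure to reproduce.

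**Assumed inputs.** 91 per arm (182 / 2); CRF in SD units; no interim CRF test, except where stated. Dropout, mean change and pre/post correlation are varied.

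**Algebra.** For each arm (E experimental, C control), let q be the fraction without a post-test, m the mean change of completers, and u the mean change dropouts would have had.
- True mean change in an arm: (1 − q)m + qu.
- Mean change under LOCF: (1 − q)m.
- LOCF error in E minus C: qC·uC − qE·uE.
- Error of an observed-data analysis that treats dropouts like completers: qE(mE − uE) − qC(mC − uC).

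**No true effect, dropouts like completers, both arms improving 0.5 SD.** With 10% dropout in E and 30% in C, the LOCF error is 0.30 × 0.5 − 0.10 × 0.5 = +0.10 SD. With the dropout fractions reversed it is −0.10 SD. The false-positive rates below are from 20,000 simulated trials per scenario. The change contrast equals a GEE group-by-time term if the GEE used filled pre/post data.

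| Dropout | Pre/post correlation | Post-test t-test | Change contrast |
|---|---|---|---|
| 10% v 30% | 0.3 | about 10% | about 10% |
| 10% v 30% | 0.5 | about 10% | about 12% |
| 10% v 30% | 0.7 | about 10% | about 16% |
| 10% v 30% | 0.8 | about 10% | about 21% |
| 10% v 30% | 0.9 | about 10% | about 33% |
| 10% v 20% | 0.7 | about 6% | 7–8% |
| 5% v 10% | 0.7 | about 5% | about 5% |
| 20% v 20% | 0.7 | about 5% | about 5% |

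The change contrast is sensitive to the correlation because a higher correlation makes the SD of change smaller, so the same 0.10 SD error is more easily detected. At 10% v 30% and correlation 0.7, the rates (post-test / change) are about 7% / 9% if both arms improve 0.3 SD, 17–18% / 29–30% if 0.8 SD, and 5% / 5% if neither arm changes.

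**A true effect of 0.418 SD, dropouts like completers, common change 0.5 SD.** Completers change 0.918 in E and 0.5 in C.
- 30% E v 10% C: 0.7 × 0.918 − 0.9 × 0.5 = 0.19 SD.
- 10% E v 30% C: 0.9 × 0.918 − 0.7 × 0.5 = 0.48 SD.
- 20% in both: 0.8 × 0.418 = 0.33 SD, that is, shrunk by the dropout fraction.

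**Dropouts unlike completers, 20% in each arm, same completer changes.**
- No dropout would have changed: LOCF error 0; observed-data error 0.2 × 0.918 − 0.2 × 0.5 = +0.08 SD.
- E dropouts worsen 0.5, C dropouts unchanged: LOCF error +0.10; observed-data error 0.2 × 1.418 − 0.2 × 0.5 = +0.18 SD.
- C dropouts worsen 0.5, E dropouts unchanged: LOCF error −0.10; observed-data error 0.2 × 0.918 − 0.2 × 1.0 = −0.02 SD.

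LOCF is the less biased method in the first two cases and the more biased in the third.

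**If an interim test exists.** Suppose every dropout had an interim CRF value at half the eventual change. The 10% v 30% rates (0.5 SD, correlation 0.7) then fall from about 10% / 16% to about 6% / 7%.

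**The case against.** The strongest reply is that harm to this trial is not shown. With equal dropout, with 5% v 10%, or with no common change, the false-positive rate stays near 5%. Material inflation needs both a large dropout gap and a sizeable common change, and the document reports neither. This stands, and it limits the point to an untested assumption of unknown consequence.

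A second reply is that the GEE on longitudinal data may have used interim visits or observed data only. Either is possible. The zero-change statement is therefore conditional on there being no interim CRF test. But the plan states neither, so the GEE cannot be credited as a check on LOCF. Equally, the document does not show that the GEE inherited the LOCF values.

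A third reply is that the alternatives also rest on an assumption, missing at random, and can be further off than LOCF, as two of the three cases above show. That is right. It is why replacing LOCF with another single method would not be enough, and why, once the analysis is done, LOCF should not be displaced as the pre-stated result.

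A reader might go further and infer that LOCF favoured the experimental group, that the CRF result is wrong, or that LOCF is always the worse method. The document supports none of these. It gives no dropout by arm and no CRF data, and the sign of the error depends on both.

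**Conclusion.** The point holds in conditional form and should be fixed. LOCF is the sole stated rule for the ITT analysis and no sensitivity analysis is planned; both facts are plain from the text. If CRF was measured only before and after, the rule imputes zero change for every missing post-test, with an error of qC·uC − qE·uE that can go either way. The error is nil when dropouts would not have changed, or when the two terms cancel.

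Confidence is high about the omission and the mechanism. The size here cannot be determined. The simulated rates are illustrations that rest on 91 per arm, dropout unrelated to outcome within arm, and the assumed changes and correlations. The change-contrast figure in particular should be read as a range and not as a single value.

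**What to change.** 1. Analyse CRF with a baseline-adjusted, likelihood-based mixed model on all observed data, or with multiple imputation by arm followed by the planned GEE. An unweighted GEE on incomplete data should not be relied on alone.
2. Accompany it with a delta-adjusted analysis: shift the imputed CRF of dropouts by delta, varied separately by arm. The range should cover zero (missing at random), minus each arm's completer mean change (the LOCF assumption), worsening beyond that, and upward shifts. Report the delta pairs at which the conclusion changes.
3. Keep LOCF as a labelled sensitivity analysis. If the analysis is already done, as the past tense of the document suggests, keep LOCF as the pre-stated result and report the new model and the delta analysis beside it as dated, disclosed post hoc analyses.
4. Report the number of missing post-tests and the reasons by arm, whether any interim CRF test exists, and whether the GEE used LOCF-filled data.

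The cost is a modest re-analysis of data already held, with no new participants or measurements. The plan names one package ("Statistical analyses were performed using SPSS version 16.0 software"); if it cannot do the imputation steps, a second is needed. The new model relies on missing at random, an assumption that the delta analysis is there to test.

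### No baseline adjustment is stated for the between-group comparison of CRF or the continuous secondary outcomes, and the GEE terms are not given

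*Combined protocol and SAP*

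**What the plan says.** The whole analysis plan is one paragraph, and three of its sentences bear on how groups and time points are compared:

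- Within group: "Paired t-tests were used to compare pre- and post-tests". This does not compare the arms.
- Between groups: "Student's t-tests and chi-squared tests examined pre- and post-intervention differences between groups". For continuous outcomes this is a t-test. The sentence can mean separate tests at each time point or a test of pre-to-post change.
- Longitudinal: "Generalized estimating equations (GEEs) were used to analyze longitudinal data, considering within-participant correlation". No group, time, interaction or baseline term is listed, and no working correlation.

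For missing values the plan says: "Missing data were handled using the last-observation-carried-forward method for intent-to-treat analysis". The Objective(s) paragraph makes CRF the primary outcome. No sentence says whether the t-test or the GEE is its primary analysis, and no covariate or ANCOVA is mentioned anywhere. The Methods paragraph gives the size of the trial: "Eligible participants with long COVID ($n = 182$) were randomly assigned in a 1:1 ratio".

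**The concern.** Pre-tests are collected, and a baseline value usually predicts its post value well. A t-test cannot use that information as a covariate on either reading of the sentence. Whether the GEE uses it depends on terms the plan omits:

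- With group, time and group-by-time terms and free baseline means, the interaction is the difference in mean change, so the GEE has change-score precision.
- With baseline as a covariate, or with one baseline mean common to both arms, it has ANCOVA precision.

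Type I error over randomisations is not at stake. What is at stake is a wider interval for CRF than the data allow, and an estimate that moves with any chance baseline difference. Post-only and change estimates move in opposite directions, so the stated analyses can disagree, and no rule says which one decides.

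**Working it through.** **Inputs from the document.** 182 randomised 1:1 (Methods), taken as 91 per arm; two-sided 0.05 (Statistical analysis plan). The figure of 182 has no effect size, SD, power or dropout behind it, so it cannot be reproduced.

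**Assumptions.** The document gives no pre-post correlation ρ, SD, effect size, dropout rate or number of visits. I take one follow-up, equal pre and post SD, and ρ = 0.3, 0.5, 0.7, 0.8. Results are in SD units.

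**1. What each GEE form estimates.** GEEs were fitted to 400 simulated trials per ρ. The free-baseline interaction equalled the difference in mean change to within 4e-16. The GEE of post values with baseline as covariate equalled ANCOVA to within 5e-15. The common-baseline GEE had the same spread as ANCOVA (about 0.146 at ρ 0.3 and 0.109 at ρ 0.7), against 0.183 and 0.117 for change.

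**2. Variance of the group difference, relative to post-only.** Post-only 1; change 2(1−ρ); ANCOVA 1−ρ². Change minus ANCOVA is 2(1−ρ) − (1−ρ²) = (1−ρ)², which is never negative. Estimating the slope costs ANCOVA a finite-sample factor k = 1 + 1/178 = 179/178. With it, ANCOVA beats post-only when ρ > √(1−1/k) = 0.075, and beats change when ρ < 2/k − 1 = 0.989.

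**3. Sample size and interval width.** To match ANCOVA on 182, post-only needs 182/(1−ρ²) and change needs 182 × 2/(1+ρ). Including k would lower these by about 0.6%. The 95% half-width is t × √(2/91) × the SD factor (the square root of the variance in step 2), with √(2/91) = 0.148.

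| ρ | 0.3 | 0.5 | 0.7 | 0.8 |
|---|---|---|---|---|
| Relative variance, change | 1.40 | 1.00 | 0.60 | 0.40 |
| Relative variance, ANCOVA | 0.91 | 0.75 | 0.51 | 0.36 |
| Matching N, post-only | 200 | 243 | 357 | 506 |
| Matching N, change | 280 | 243 | 214 | 202 |
| Half-width, post-only | 0.29 | 0.29 | 0.29 | 0.29 |
| Half-width, change | 0.35 | 0.29 | 0.23 | 0.19 |
| Half-width, ANCOVA | 0.28 | 0.25 | 0.21 | 0.18 |

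**4. Power (noncentral t; effect sizes assumed).**

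| ρ | 0.3 | 0.5 | 0.7 | 0.8 |
|---|---|---|---|---|
| 0.30 SD: post-only | 52% | 52% | 52% | 52% |
| 0.30 SD: change | 40% | 52% | 74% | 89% |
| 0.30 SD: ANCOVA | 56% | 64% | 80% | 92% |
| 0.50 SD: gain over post-only (points) | 2 | 5 | 8 | 8 |
| 0.50 SD: gain over change (points) | 13 | 5 | 1 | 0 |

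At 0.30 SD the gains are 4/12/28/40 points over post-only and 16/12/7/3 over change.

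**5. Chance baseline difference.** Its standard error is 0.148 SD, so P(|difference| ≥ 0.2 SD) = 2(1 − Φ(0.2/0.148)) = 0.177. A difference of 0.2 SD shifts the post-only estimate by 0.2ρ = 0.06/0.10/0.14/0.16 SD. It shifts the change estimate by 0.2(1−ρ) = 0.14/0.10/0.06/0.04 SD the other way. ANCOVA is not shifted.

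**6. Effect of LOCF.** If a random fraction q drops out and baseline is copied forward, ρ becomes q + (1−q)ρ. That gives 0.37/0.55/0.73/0.82 at q = 0.10 and 0.44/0.60/0.76/0.84 at q = 0.20. At q = 0.20 the ANCOVA variance is 81/64/42/29% of post-only and 72/80/88/92% of change. All three estimates shrink to (1−q) of the effect, which adjustment does not repair. Simulated type I error at ρ 0.7 stayed between 0.047 and 0.051 for all three methods, with no dropout and at q = 0.20.

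**The case against.** The strongest reply is that the plan does name a GEE. If that model carried baseline as a covariate or a common baseline mean, there is no loss, and the text then shows only under-specification. This stands, and it is why the finding is that adjustment is not stated, not that it was absent.

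Second, the largest gains (28 and 40 points) need a post-only t-test, an assumed 0.30 SD effect and ρ of 0.7 to 0.8. Against change at those correlations the gain is 7 and 3 points, and at 0.50 SD it is 1 and 0. Large gains over both comparators cannot occur together. This also stands.

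Third, equal variances are an assumption. If the post SD were 1.25 times the pre SD, the ANCOVA variance would be 89%, 98% and 100% of the change variance at ρ 0.5, 0.7 and 0.8, instead of 75%, 85% and 90%. If the post SD were smaller than the pre SD, the gain over change would be larger. So the size of the gain over change is uncertain. The direction is not: apart from the small finite-sample cost, ANCOVA is never less precise.

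Fourth, the plan is in the past tense and dated 2023.11.25, so an added model may be post hoc. This governs how the model is labelled and does not remove the gap in the plan.

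**Conclusion.** The concern holds. No baseline adjustment is stated for CRF or the continuous secondary outcomes, the GEE terms are missing, and no primary CRF analysis is named. If the CRF conclusion rests on a t-test or a free-baseline GEE, it is valid and unbiased over randomisations but less precise than it could be. With equal variances and 91 per arm, this is so for any ρ from about 0.075 to 0.989.

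The loss ranges from negligible (against change at high ρ or a large effect) to substantial (against post-only at high ρ, or against change at low ρ). It is zero if the GEE already adjusts. The exact size cannot be fixed, because the document gives no correlation, SD, effect size or dropout rate. I rate this as something the sponsor should change. It does not invalidate the trial.

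**What to change.** Name one primary CRF analysis: the post-intervention group difference, with its 95% CI, from one of these:

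- a model with baseline CRF as covariate (ANCOVA, or a GEE of post-baseline values with baseline as covariate);
- a longitudinal model with a baseline mean common to both arms.

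Use the same form for each continuous secondary outcome with its own baseline. Keep the unadjusted t-tests as supportive and say whether they use post values or change. If the GEE already had one of these forms, list its terms and name it as primary.

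The cost is one model term, one degree of freedom and a few sentences; no new data are needed. If outcome data had been seen before the model was chosen, it cannot count as prespecified. Label it a later specification and report the originally stated t-test and GEE results beside it.
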